Aim 3: to examine differences in patient satisfaction and quality of life following retropubic midurethral sling placement between women receiving retropubic normal saline vs lidocaine at time of midurethral sling placement. Differences in patient satisfaction will be compared using multiple questionnaires at multiple time points. Patients will be asked to complete the American Pain Society Patient Outcome Questionnaire (APS-POQ-R) on POD #1. Patients will be asked to rate their satisfaction with surgery on a Likert scale (with 1 being the least satisfied and 5 being the most) at their 6-week postoperative follow up visit. We hypothesize that women receiving normal saline for hydrodissection will have improved patient satisfaction, mood, and quicker return to activities, as evidenced by lower APS- POQ-R scores and higher Likert scores compared to those receiving lidocaine.

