#### Patient satisfaction and mood

APS-POQ-R: The APS-POQ-R is a validated questionnaire used to assess QOL and satisfaction with pain control over the 24 hours following an operation. It is preferred over more global measures of QOL since it is validated for acute pain in the setting of recent surgery. This questionnaire was designed to assess satisfaction with pain control and impact of pain on mood and emotional well-being. It contains twelve items across six subscales: pain severity and relief, impact of pain on mood/emotions, adverse effects, satisfaction, participation in decision making, and non-pharmacological methods of pain management. We are specifically interested in the impact of pain on satisfaction (item 9), mood/emotions (item 5 a-d) and adverse effects (item 6 a-d, see below). These subscales use a 0-10 rating scale. This measure has good internal consistency (alpha=0.85) and validity.

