## **Data and Statistical Methods**

**Aim 1**: to compare the incidence of urinary retention following retropubic midurethral sling placement in those women receiving normal saline vs lidocaine for retropubic hydrodissection. Rates of postoperative urinary retention will be compared between groups using chi squared testing. Duration of urinary retention measured in days will be compared using t-tests or nonparametric testing as appropriate. To adjust for other factors that may impact voiding trial results, logistic regression analysis will be performed and will include variables identified as significant (p>0.01) on univariable analysis as well as intraoperative narcotic use, age, and estimated blood loss. All analyses will be performed using intention to treat. Data analyses will be done using SPSS and Matlab.

**Aim 2**: to assess postoperative pain in women receiving retropubic normal saline vs lidocaine during midurethral sling placement. VAS scores will be measured on a scale of 0-100mm with higher scores indicating worse pain. Change from baseline in VAS pain scores will be compared at each time point with t-tests. Narcotic requirements measured in morphine equivalent grams will be compared by t-tests (and

Wilcoxon rank-sum tests if non-parametric). Both VAS pain scores and narcotic requirements will be compared in an intention to treat analysis. Multivariable logistic regression analyses will be used to identify independent risk factors that predict pain at 2, 6 and 24 hours postoperatively. We plan to adjust for operating time, estimated blood loss, urinary retention, and concomitant procedures, as all of these may predict worse postoperative pain. Anything found to be different at baseline will also be included as covariates.

**Aim 3**: to assess patient satisfaction in women receiving retropubic normal saline vs lidocaine during midurethral sling placement. Patient satisfaction Likert scale questionnaires will be compared using t-tests with lower scores indicating worse satisfaction. T-tests (and Wilcoxon rank-sum tests if non-parametric) will be used to analyze results of individual APS-POQ-R questions.

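### Aim 3 tests single APS-POQ-R questions with no lead test; one mood score from items 5a-d would serve the stated hypothesis better, a minor secondary-outcome improvement

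*Combined protocol and SAP*

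**What the plan says.** The Aim 3 paragraph of Data and Statistical Methods gives the whole analysis of this questionnaire in one sentence: "T-tests (and Wilcoxon rank-sum tests if non-parametric) will be used to analyze results of individual APS-POQ-R questions". It does not say which questions, and it defines no combined score.

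Two other places describe the outcome at a higher level:

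- Aim 3 in Background/Hypothesis expects better satisfaction, better mood and a faster return to activities with saline, "as evidenced by lower APS- POQ-R scores and higher Likert scores compared to those receiving lidocaine".
- The Patient satisfaction and mood section says of the instrument: "It contains twelve items across six subscales". It then states a specific interest in "satisfaction (item 9), mood/emotions (item 5 a-d) and adverse effects (item 6 a-d", adds "These subscales use a 0-10 rating scale", and supports the choice of instrument with "This measure has good internal consistency (alpha=0.85) and validity".

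Table 1 likewise lists the questionnaire by domain, with side effects on one row and satisfaction and mood on another. Nowhere do the documents name a lead APS-POQ-R question, set a multiplicity rule or label these tests exploratory.

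**The concern.** The hypothesis concerns mood and satisfaction as constructs, but the planned tests concern single questions. Two things follow.

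First, the plan has no rule for moving from nine or more p-values to a statement about Aim 3. With several tests at the usual level, an isolated significant question is fairly likely even if the treatments do not differ, and the plan does not say what such a result would mean.

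Second, mood is measured by four questions. If treatment moves them together, their mean is a more precise measure than any one of them. Internal consistency, which the protocol cites in favour of the instrument, is a property of a multi-item score and lends no support to single-question tests.

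What is at stake is how a secondary result can be interpreted, not the trial's main conclusion.

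**Working it through.** **Inputs from the documents.** Satisfaction has one question (9), mood four (5a-d) and adverse effects four (6a-d): 1 + 4 + 4 = 9. The Sample Size Calculation gives 72 per group and a two-sided 5% level, both for the primary outcome only.

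**Assumptions.** The 5% level applies to each question. Within-domain correlation lies between 0.3 and 0.8. The illustrative effect is a shift of 0.4 single-question SD on every mood item. The documents give none of these for the APS-POQ-R.

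**The plan's own figure.** There is no error rate or power for Aim 3 to reproduce. The 72 per group used below is consistent with its stated basis: 35% against 15%, 80% power and two-sided 5% give 73 with pooled variance and about 70 with unpooled variance.

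**False positives**

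- Nine independent tests: 1 − 0.95^9 = 0.370. Expected number of false positives: 9 × 0.05 = 0.45.
- Nine tests correlated only within domains (simulation of z-tests in blocks of 4, 4 and 1): 35% at r = 0.3, 30% at r = 0.6, 25% at r = 0.8.
- If all twelve items were tested as twelve independent tests, which the sentence does not rule out: 1 − 0.95^12 = 0.460.
- The four mood questions alone, if independent: 1 − 0.95^4 = 0.185. One mood score: 0.05.
- For comparison, three domain tests, if independent: 1 − 0.95^3 = 0.143. Moving to domains does not control error by itself, so a lead test has to be named.

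**Precision of a mood score**

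The SD of a four-item mean, relative to one item, is √((1 + 3r)/4). The standardised effect on the mean is 0.4 divided by that. Power is from the noncentral t with 2 × 72 − 2 = 142 df at two-sided 5%.

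| Measure | Relative SD | Effect | Power |
|---|---|---|---|
| One question | 1.00 | 0.40 | 66% |
| Mean of 5a-d, r = 0.3 | 0.69 | 0.58 | 93% |
| Mean of 5a-d, r = 0.586 | 0.83 | 0.48 | 82% |
| Mean of 5a-d, r = 0.8 | 0.92 | 0.43 | 73% |

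The middle value is 0.85/(4 − 3 × 0.85) = 0.586. It is what the cited alpha implies if that alpha belongs to a four-item scale, which the protocol does not say.

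**When only one item moves**

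If one question shifts by 0.4 SD and the other three do not, the mean shifts by 0.4/4 = 0.1. Its standardised effect is 0.1/0.69 = 0.145 at r = 0.3 and 0.1/0.92 = 0.108 at r = 0.8. Power is then about 14% and 10%, against 66% for that question tested alone.

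**The case against.** The strongest reply has four parts.

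- **No strict contradiction.** A reader might infer that the two sections conflict outright. They do not. The Patient satisfaction and mood section names its interest by item number, which is compatible with item-level analysis, and no section promises a subscale score. The mismatch is one of level: the hypothesis and the description speak of scores and subscales, and the analysis of questions. This part of the reply stands.
- **Not every domain gains.** A reader might infer that all three domains should become scores. Satisfaction is a single question, so nothing is gained there. Side effects are often of interest one at a time, because a treatment may change one and not the others. The dilution result shows that averaging 6a-d could hide such a change. This stands too, so the case for a score is confined to mood.
- **The power gain is assumed.** It needs a common shift and a full 5% level. If the level were split over three scores (0.05/3 at Holm's first step), a four-item mean would have 73% power at r = 0.5 and 68% at r = 0.586, close to the 66% for one uncorrected question. The gain therefore holds only for a single pre-named test.
- **These are third-aim outcomes.** The protocol sets no error control for any secondary outcome, and it never says that one significant question would establish Aim 3. A reader might infer such a rule, but it is not in the text. This limits the weight of the point. It does not remove the need to say how the tests will be read.

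**Conclusion.** The point holds as a modest improvement to a secondary analysis. As written, the plan allows at least nine separate tests with no stated reading. The chance of at least one false positive is 37% under independence and about 25-35% for within-domain correlations of 0.8-0.3, taking 5% per test as an assumption. A single pre-named mood score fits the stated hypothesis better. Under the assumed common 0.4 SD shift it raises power from 66% to about 73-93%. Those powers show direction and rough size only.

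The documents do not support a claim that the primary comparison or the sample size is affected, because both rest on voiding trial failure alone.

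**What to change.** Rewrite the APS-POQ-R sentence under Aim 3, before unblinding, to say:

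1. Mood is scored as the mean of items 5a-d, and the comparison of this score is the lead APS-POQ-R test for Aim 3. It replaces the four separate mood tests.
2. Item 9 is analysed on its own as the satisfaction measure, with its scoring direction stated. The Aim 3 hypothesis expects improvement to show as lower scores, and the documents do not say how item 9 is anchored. It should not be pooled with other items.
3. Items 6a-d are reported one by one as side effects, labelled exploratory, and are not averaged.

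The cost is one edited sentence and no new data. The trial gives up confirmatory claims on single mood questions, and it loses power if treatment changes only one of the four.

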## **Data and Safety Monitoring Plan**

A data safety monitoring board will be established which shall consist of the co-investigators annually submitting safety and AE information to the IRB. In addition, we will proactively monitor for allergic reaction to lidocaine, epinephrine, and normal saline throughout the first 6 hours following surgery. Hospital readmission will be proactively monitored through POD #7. We will also monitor closely for heightened rates of postoperative urinary retention. As mentioned previously, approximately 10-50% of women experience acute postoperative urinary retention. Should this number exceed 80% (assessed via administration of standardized retrograde voiding trial) in those women receiving retropubic normal saline, we would consider stopping further study enrollment pending further investigation.

Furthermore, an interim analysis will be performed at 12 weeks and/or following the enrollment of 30 subjects, whichever event comes sooner. At that time, we plan to investigate the presence of any serious events like blood transfusions or operating room take backs. We also plan to run a preliminary analysis on the rate of failed voiding trials between the two study arms. This report is to be reviewed by the IRB.

